#### **7.4. Prior and Concomitant Medications**

Summaries of (a) Prior Basal Cell Carcinoma Medications using the safety population, (b) Prior Medications Excluding Prior Basal Cell Carcinoma Medications using the safety population, and (c) Concomitant Medications using the full analysis population will be provided.

For each summary, the total number of medications, the number and percentage of subjects with at least one medication, and the number and percentage of subjects with at least one medication categorized by Anatomical Therapeutic Chemical (ATC) Classification (ATCC) and Preferred Name (PN) will be provided. ATC Level 4 will be displayed, but if not available, the nearest available parental ATC Level will be displayed. Subjects having more than one medication may appear in more than one ATCC or PN but will be counted at most once per each ATCC and PN. ATCC and PN will be displayed in order of decreasing frequency of total ATCC count, followed by decreasing frequency of total PN count, and then alphabetically if tied.

Prior medications are defined as medications recorded in EDC as pre-study medications. Concomitant medications are defined as medications that are not recorded in EDC as pre-study medications, as well as medications with unknown or undeterminable start dates.

Separate listings will be provided for the following using the safety analysis population:

- Prior Basal Cell Carcinoma Medications (Medications to Report (Yes, No), Prior Therapy, Total Daily Dose, Dose Unit, Frequency, Route, Start Date, End Date), and
- Prior and Concomitant Medications Excluding Prior Basal Cell Carcinoma Medications (Medications to Report (Yes, No), Medication/Therapy, Indication, Dose, Dose Unit, Frequency, Route, Prior or Concomitant, Start Date, End Date (or Ongoing at the End of Study), whether Medication Treated an Adverse Event (Yes, No)).

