# 7.5 Concomitant Therapy

Throughout the study, investigators may prescribe any concomitant medications or treatments deemed necessary to provide adequate supportive care except for those listed in Section 7.6.1.

All concomitant medications administered while the subject is enrolled in the study (including over-the-counter products) must be recorded on the eCRF, listing generic name or trade name, indication, quantity administered, and date(s) of administration.

Hormonal birth control pills or hormonal replacements may be taken during the course of this study. If necessary, acetaminophen may be administered at the investigator's discretion in single doses of up to 2 g/day. Prophylactic antibiotics may be prescribed and/or administered by the investigator in advance of excision of any target and nontarget lesions.

For itching of the treated areas, subjects are permitted to use gentle topical agents (e.g., Aquaphor®, CeraVe®) that will not irritate the skin in these areas.

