## **6. Analysis Populations**

**Enrolled Subjects:** Enrolled subjects are subjects who signed the informed consent form and were not screen failed. Enrolled subjects will serve as the population for certain analyses as described in this SAP.

**Safety (SAF) Population:** The Safety Population will include all subjects who received at least one injection of VP-315. The SAF Population will serve as the primary population for the analysis of safety-related data.

**Full Analysis (FA) Population:** The Full Analysis Population will include enrolled subjects who received one full dose (actual equals expected for at least one treated lesion) of VP-315 (for Part 1 and Part 2 Cohorts 4 and 5, a full dose consists of two injections) and have at least one non-missing post-baseline efficacy observation for histologic clearance of lesions at excision (see Section 8 of this SAP for details). The FA Population will serve as the primary population for the analysis of efficacy-related data.

**Per-protocol (PP) Population:** The Per-protocol Population will include FA subjects who have no major protocol deviations that may substantially affect the results of the efficacy analyses outlined in Section 8 of this SAP. The final determination on protocol violations, and thereby the composition of the PP, will be made before database lock.

The PP Population will be used as the secondary population for the efficacy analyses outlined in Section 8 of this SAP.

A non-exhaustive list of potential major protocol deviations is provided below:

- Investigational Product Deviations
  - Subject received wrong treatment
  - Deviation in IP storage
  - Error in IP dosing
- Enrollment Deviations
  - Subject is enrolled prior to determining whether eligible for study
  - Ineligible subject is enrolled
  - Enrollment occurs outside protocol window
- Study Data and/or Forms Deviations
  - Forms or data not sent from clinical site to coordinating center
  - Missing data and/or form
  - Missing images and/or operative reports
- Subject Deviations
  - Subject administration of a prohibited medication
  - Subject compliance with protocol
  - Subject met withdrawal criteria but was not withdrawn
- Visit/Procedure Schedule Deviations
  - Visit/Procedure not completed
  - Visit/Procedure not completed in window

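### SAP 7.4 sorts medicines by a pre-study flag rather than by use during dosing, and puts only the concomitant summary on the Full Analysis population (minor)

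*SAP*

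**What the plan says.** **Classification.** SAP 7.4 states: "Prior medications are defined as medications recorded in EDC as pre-study medications". It then says that "Concomitant medications are defined as medications that are not recorded in EDC as pre-study medications", "as well as medications with unknown or undeterminable start dates". Neither document says when a site sets the pre-study flag.

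**Population.** The two prior-medication summaries in SAP 7.4 use the Safety population. For the third, the wording is "Concomitant Medications using the full analysis population will be provided". The medication listings in the same section use Safety, as do the adverse event summaries (SAP 9.1) and vital signs (SAP 9.3).

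**What separates the populations.** SAP 6 admits to Safety anyone who received an injection. FA needs one full dose for at least one treated lesion and a histologic clearance result at excision. It adds that "for Part 1 and Part 2 Cohorts 4 and 5, a full dose consists of two injections".

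**Protocol background.** Protocol 7.5 requires that "All concomitant medications administered while the subject is enrolled in the study" be entered on the eCRF. Protocol 7.6.1 has subjects stay on their existing prescriptions, apart from excluded ones.

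**The concern.** A concomitant-medication table is normally read as showing what subjects were taking while exposed to study drug, and what was given when they reacted. The SAP 7.4 rule does not answer the first question, because it turns on when a medicine was first recorded and not on whether it was still in use. Protocol 7.6.1 makes continuing medicines an expected case.

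The second question is affected by the population. FA is the SAP's primary efficacy population, and a subject can fall out of it because of a reaction that stops dosing before a full dose is complete. That subject's event would be counted in the adverse event tables, while any medicine given for it would not be counted in the concomitant table.

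This matters because safety and tolerability are the primary objectives. Hypotension is one of the criteria for a treatment-related adverse event of special interest (Protocol 10.2), and Protocol 2.2.2 suggests histamine release from mast cells as its cause. Long-term medicines acting on blood pressure or histamine are obvious examples of what a reader would look for, although neither document names any such medicine in use.

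**Working it through.** The plan gives no figure to reproduce, so the check applies its definitions to the possible cases.

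**Step 1: the classification rule (SAP 7.4).** Assume that the flag means the medicine was started before the study.

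| Medicine | In use at or after first injection? | Concomitant under SAP 7.4? | Agrees with actual use? |
|---|---|---|---|
| Flagged, known start, stopped before first injection | No | No | Yes |
| Flagged, known start, still taken during dosing | Yes | No (prior only) | No |
| Flagged, unknown start, still taken during dosing | Yes | Yes | Yes |
| Flagged, unknown start, stopped before first injection | No | Yes | No |
| Not flagged, started after first injection | Yes | Yes | Yes |

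Rows 2 and 3 can be the same medicine taken in the same way; only the completeness of the start date differs. Rows 2 and 4 are errors in opposite directions. Row 2 medicines do appear in the prior table, but alongside row 1 medicines, because no ongoing/stopped split is planned there.

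**Step 2: the population rule (SAP 6 with Protocol 7.3.2.2, 8.3 and 10.2).**

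| Subject | Safety | FA | New medicines for a reaction in the concomitant summary? |
|---|---|---|---|
| One full dose, reacts, stops, excised with histology | Yes | Yes | Yes |
| Split-dose regimen, stops after injection 1 and never completes a dose | Yes | No | No; listing only |
| Full dose, but no excision histology for any lesion | Yes | No | No; listing only |

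The second row can arise on the first dosing day. Protocol 10.2 ends VP-315 for a subject with a qualifying event. Protocol 7.3.2.2 allows the second injection if the reaction to the first resolves within 1 hour, but also requires injections to stop for special-interest events of Grade 2 or higher. These passages need to be reconciled by the sponsor; the point here is only that the second row is possible. SAP 7.6 provides for it by collecting adverse event as a reason for an injection not given or a full dose not received.

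**Step 3: size.** The two-injection condition covers Part 1 and Cohorts 4 and 5. With the group sizes in SAP 3, that is 10 + 36 + 37 = 83 of 10 + 82 = 92 subjects. This is the number to whom the condition applies, not the number who fail it, which is not given. For scale, suppose one subject in a reporting column (SAP 5.5) falls outside FA. In an initial cohort of 10 that removes 1/10 = 10% of the column; in the expansions of 26 and 27 it removes 1/26 = 3.8% and 1/27 = 3.7%. If nobody falls outside FA, the loss is zero.

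**The case against.** Several stronger readings are tempting, and the documents do not support them.

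- **That continuing medicines are lost from the outputs.** They are not. A flagged medicine is in the prior table on Safety. The Safety listing shows each medicine with its indication, dates or ongoing status, and whether it treated an adverse event.
- **That every continuing medicine is affected.** Unknown start dates are exempt. The rest depends on a flagging rule that neither document gives: if sites flag only medicines already stopped, the first problem largely disappears.
- **That early reactors as a group drop out.** FA needs one full dose, not a completed course. Protocol 8.3 requires excision from subjects who stop treatment early, so most of them can have histology. The SAP's two-injection condition does not extend to Part 2 Cohorts 1 and 2.
- **That hypotension rates cannot be read against background medication.** A count by drug class does not link a medicine to an event under any definition. That link needs subject-level data, and the Safety listings of medicines, blood pressure and adverse events provide it.
- **That the SAP departs from the protocol without saying so in SAP 14.** Protocol 7.5 is an instruction on what to record. Protocol 11.5 plans no medication summary, so there is nothing for SAP 14 to list.

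All five objections stand and narrow the point. They leave two things in place: the rule ignores use during dosing, and this one summary is on a different population from its companion tables without a stated reason. A listing lets a reader rebuild the table by hand; it does not correct the table.

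**Conclusion.** The point holds as a minor defect. Followed as written, SAP 7.4 gives a concomitant table that misstates use during treatment in both directions, and a denominator that need not match the adverse event tables.

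The first part assumes that the pre-study flag is set for medicines that began before the study and continue into it. That is a natural reading, but it is not confirmed. The second part rests only on the stated population definitions. Its practical size depends on how many Safety subjects are outside FA, which is unknown and may be zero. The study is descriptive, and no efficacy or safety endpoint or cohort decision uses this table.

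**What to change.** In SAP 7.4:

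1. Define a concomitant medication as any medication taken on or after the first injection. That means it started on or after the first injection, or started earlier and either ended on or after the first injection or was ongoing.
2. State that a medicine may count as both prior and concomitant.
3. Run the concomitant summary on the Safety population, as for the prior-medication summaries.

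The start date, end date or ongoing status, and adverse-event-treatment indicator are already in the planned listing, so no new data are needed. The cost is a few sentences, one changed derivation and a longer concomitant table. If the database is already locked, the revised table can be added and labelled post hoc, as SAP 5.2 provides.

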## 7.5. Medical History

Summaries of (a) Prior Basal Cell Carcinoma Treatment, Procedures, and Surgeries and (b) Medical History Excluding Prior Basal Cell Carcinoma Treatment, Procedures, and Surgeries will be provided using the safety population.

For the Medical History Excluding Prior Basal Cell Carcinoma Treatment, Procedures, and Surgeries summary, the total number of events, the number and percentage of subjects with at least one event, and the number and percentage of subjects with at least one event categorized by system organ class (SOC) and preferred term (PT) will be provided. Subjects having more than one event may appear in more than one SOC or PT but will be counted at most once per each SOC and PT. SOC and PT will be displayed in order of decreasing frequency of total SOC count, followed by decreasing frequency of total PT count, and then alphabetically if tied.

For the Prior Basal Cell Carcinoma Treatment, Procedures, and Surgeries summary, the total number of events, the number and percentage of subjects with at least one event, and the number and percentage of subjects with at least one event categorized by Reported Term (RT) (Curettage, Electrodesiccation, Excision, MOHS, Topical Treatment, Other), will be provided. Subjects having more than one event may appear in more than one RT but will be counted at most once per each RT. RT will be displayed in order of decreasing frequency of total RT count, and then alphabetically if tied.

Separate listings using the safety population will be provided for the following:

- Prior Basal Cell Carcinoma Treatment, Procedures, and Surgeries (Prior Events to Report (Yes, No), Previous Treatment Received (Curettage, Electrodesiccation, Excision, MOHS, Topical Treatment, Other), Most Recent Treatment Received, Date of Most Recent Treatment), and

- Medical History Excluding Prior Basal Cell Carcinoma Treatment, Procedures, and Surgeries (Any Relevant Medical or Surgical History (Yes, No), Diagnosis, Condition or Surgery, Onset Date, Resolution Date (or Ongoing)).

## 7.6. Administration of Study Treatment

A summary of Administration of Study Treatment will be provided using the safety population.

Descriptive statistics will be provided for the following parameters:

- Total Daily Target Volume (cc),
- Total Daily Target Dose (mg),

And for each injection (Injection 1, Injection 2) within each lesion (TL1, TL2):

- Expected Injection Volume (cc),
- Actual Injection Volume (cc),
- Expected Injection Dose (mg), and
- Actual Injection Dose (mg).

The number and percentage of subjects will be provided for the following parameters:

- Study Drug Reconstituted (Yes, No).

The summary will present injection (Injection 1, Injection 2) within lesion (TL1, TL2) within scheduled visit (W1D1, W1D2, W1D3, W2D1, W2D2, W2D3).

A separate listing will be provided using the safety population for the Administration of Study Treatment, and the listing will include the parameters described as above, as well as the following parameters (not all parameters were collected at all visits):

- Lesion (to be) Injected,
- Lesion Necrosed (Yes, No, Not Applicable),
- Injection Number (1, 2),
- Injection Administered (Yes, No),
- Reason Injection Not Administered (Adverse Event, Drug Permanently Withdrawn, Investigator Decision, Subject Declined, Other),

- Received Full Dose (Yes, No),
- Dose Received if Not Full Dose,
- Reason Full Dose Not Received (Adverse Event, Drug Permanently Withdrawn, Investigator Decision, Subject Declined, Other), and
- Visit, and Date and Time of Injection.

## 8. Efficacy Analysis

The conventions of Section 5 of this SAP will be applied. Tables and figures will be prefixed with 14, and listings will be prefixed 16. Tables will be provided for Part 1 and Part 2 unless noted otherwise.

Each subject can have at most two distinct target lesions (TL1, TL2) and at most three distinct non-target lesions (NTL1, NTL2, NTL3). All subjects are to have TL1, but not every subject will have additional lesions. The efficacy table summaries will be provided by subject lesion.

### 8.1. Histologic Clearance of Treated Lesions at Excision

Histologic clearance means no residual tumor seen on dermatopathological inspection, i.e., the estimate of viable tumor within estimated volume of the entire tumor bed provided by the dermatopathologist and captured in EDC is zero. When the estimated remaining tumor volume is zero, the histologic diagnosis should be scar.

A summary of histologic clearance will be provided using the histologic diagnosis of excised treated lesions (TL1, TL2) from the end-of-treatment (EOT) visit. The histologic diagnosis categories are as follows:

- Micronodular
- Nodular
- Superficial
- Superficial and Nodular
- Scar

The summary will use the full analysis population, and for each treated lesion, the number and percentage of subjects falling into each histologic diagnosis category will be provided in the summary. The summary will also be run using the per-protocol population as outlined in Section 6 of this SAP.

A separate listing will also be provided for the Excision of all lesions (TL1, TL2, NTL1, NTL2, NTL3) using the enrolled subjects, and this listing will include Lesion Number, Visit, Excision Date, Location, Histologic Diagnosis, Date of Review, Estimate of Remaining Tumor Volume, and Specimen Gross Description.

## 8.2. Clinical Clearance of Treated Lesions at Excision

Clinical clearance means no residual tumor seen on clinical visual inspection.

A summary of clinical clearance will be provided using the Physician Global Assessment (PGA) of treated lesions (TL1, TL2) at the EOT visit. The PGA is an assessment of improvement that occurs post-baseline, where reported values were to be reported as change since pre-treatment. Due to the nature of the EDC form, some reported values may be reported as change since previous visit. As it is not possible to distinguish with 100% accuracy whether the reported changes were from pre-treatment or previous visit, the PGA data will be summarized as reported. The PGA categories are as follows:

- 100% Improvement, No Visible Tumor
- 75% to < 100% Improvement
- 50% to < 75% Improvement
- 25% to < 50% Improvement
- Up to 25% Improvement
- No Change
- Worse
- Not Applicable

The summary will use the full analysis population, and for each treated lesion, the number and percentage of subjects falling into each PGA category will be provided in the summary. The summary will also be run using the per-protocol population as outlined in Section 6 of this SAP.

A separate listing will also be provided for the PGA of all lesions (TL1, TL2, NTL1, NTL2, NTL3) using the enrolled subjects, and this listing will include whether a PGA was Performed (Yes, No), Visit, Date Assessment Performed, and lesion assessments per the PGA categories as described above.

### **8.3. Estimate of Remaining Tumor Volume and Reduction in Tumor Volume at Excision**

Protocol endpoints reference that the estimated remaining tumor volume would be necrotic cells:tumor cells. However, estimated remaining tumor volume is the estimated volume of residual viable tumor cells. The assessment in the EDC is expressed as a percentage of viable tumor cells within the tumor bed which is composed of tumor cells (viable and necrotic), fibrosis, and inflammation.

A summary of the estimated remaining tumor volume (0 = None Remaining to 100 = All Remaining) will be provided using descriptive statistics for excised lesions (TL1, TL2, NTL1, NTL2, NTL3) from the end-of-treatment (EOT) visit. A 95% confidence interval for the mean estimated remaining tumor volume will also be provided in the summary using a one sample, two-sided t-test. Summary measures will be repeated for reduction in tumor volume (0 = No reduction to 100 = None Remaining).

The summaries will use the full analysis population, and for each lesion, descriptive statistics will be provided in the summary. The summaries will also be run using the per-protocol population as outlined in Section 6 of this SAP.

A separate listing will be provided for the excision of all lesions as described in Section 8.1 of this SAP.

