Appendix 5 Scar Cosemesis and Rating Scale (SCAR)9		

# GLOSSARY OF ABBREVIATIONS AND DEFINITION OF TERMS

Abbreviation or Term	Definition/Explanation
AE	adverse event
BCC	basal cell carcinoma
BMI	body mass index
BP	blood pressure
CFR	Code of Federal Regulations
CRA	Cutaneous Reaction Assessment - also - clinical research associate
CRF	case report form
CTCAE	Common Terminology Criteria for Adverse Events
DLT	dose-limiting toxicity
ECG	Electrocardiogram
eCRF	electronic case report form
EOS	end of study (visit)
ЕОТ	end of treatment (visit)
ET	early termination (visit)
F/U	follow-up (visit)
FAS	full analysis set
FDA	Food and Drug Administration
GCP	Good Clinical Practice
gDNA	Genomic deoxyribonucleic acid
hCG	beta human chorionic gonadotropin
HR	heart rate
ICF	informed consent form
ICH	International Council for Harmonisation
IRB	Institutional Review Board
IV	Intravenous
MMS	Mohs micrographic surgery

Abbreviation or Term	Definition/Explanation
MTD	maximum tolerated dose
NCI	National Cancer Institute
NMSC	nonmelanoma skin cancer
NOAEL	no observable adverse effect level(s)
Nontarget Lesion	BCC lesion to be observed for abscopal effect
Nontreated Lesion	Target lesion that was not treated with VP-315
PGA	Physician's Global Assessment
PK	pharmacokinetic(s)
PPS	per-protocol analysis set
SAE	serious adverse event
SAP	statistical analysis plan
SCAR	The Scar Cosmesis Assessment and Rating (SCAR) Scale
SCAR-Q	Scar Cosmesis Assessment and Rating Questionnaire
SRC	Safety Review Committee
Target Lesion	BCC lesion identified for treatment
Treated Lesion	Target lesion that was treated with VP-315
TEAE	treatment-emergent adverse event
TRAE	treatment-related adverse event
TRAE SI	treatment-related adverse event of special interest
US	United States
W1D1	Week 1/Day 1
WFI	water for injection

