## 5.4 BCC Lesion Eligibility

Eligible lesions are those that meet the BCC lesion eligibility specifications described herein, from samples that are either from:

- *HISTORICAL* punch or shave biopsies (i.e., samples collected according to clinical standard of care collected within the 90 days prior to W1D1);
- A 2-mm punch biopsy collected within 90 days of W1D1 for suspected BCC ≥0.5 cm to 1.0 cm, and 3-mm punch biopsy for suspected BCC >1.0 cm to 2.0 cm; or
- A shave biopsy performed according to standard of care to include superficial or middle papillary dermis collected within 90 days of W1D1.

Lesions must meet the following criteria to be eligible for treatment with VP-315 as target lesions or for observation as nontarget lesions. Up to 2 target lesions may be treated, and any eligible lesions that do not receive treatment (up to 3) will be tracked as nontarget lesions for abscopal effect.

Lesions that meet the inclusion criteria and are only excluded by Criteria 6 through 9 in Section 5.4.2 below (TARGET LESION EXCLUSION) may be tracked as nontarget lesions. Lesions that do not meet the inclusion criteria or are excluded by BCC Lesion Exclusion Criteria 1 through 5 below will not be treated or observed (i.e., ineligible) and should be excised after completion of the study unless otherwise clinically indicated.

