## 2. Objectives and Endpoints

The following objectives and endpoints will be considered.

Part 1	
Primary Objectives	Endpoints

 
To assess the safety, tolerability, and maximum tolerated dose (MTD) of ascending dose strengths of VP-315
 
	
 
Discontinuations due to adverse events (AEs); occurrence of dose-limiting toxicities (DLTs)
 
Cutaneous Reaction Assessment (CRA)
 

Exploratory Objectives 
 
To evaluate the objective antitumor efficacy of VP-315
 
	
 
Histological clearance of treated lesion(s) at excision
 
Clinical clearance of treated lesion(s) as determined by visual assessment (no tumor seen upon visible inspection) at excision
 
Estimate of remaining tumor volume (necrotic cells:tumor cells) at excision
 
Estimate of reduction in tumor volume (necrotic cells:tumor cells) at excision*
 
Abscopal effect as determined by
 

	
clinical and histological clearance of nontreated lesions at excision
 
 
• Physician Global Assessment (PGA)
 

Part 2 (Cohorts 1 and 2)	
Primary Objectives	Endpoints

 
• To determine the optimal regimen for dosing 8 mg of VP-315 based on safety and tolerability
 
	
 
• Treatment-related AEs; treatment-related serious adverse events (SAEs); discontinuations due to AEs; occurrence of TRAEs of special interest
 
• CRA
 

Secondary Objectives	Endpoints

 
• To evaluate the antitumor efficacy of VP- 315
 
	
 
• Clinical clearance of treated lesion at excision as determined by visual assessment (no residual tumor seen on visual inspection)
 
• Histological clearance of treated lesion(s) at excision
 
• Abscopal effect as determined by clinical and histological clearance of nontreated lesions at excision if nontreated lesions exist
 
• Estimate of remaining tumor volume (necrotic cells:tumor cells) at excision
 
• Estimate of reduction in tumor volume (necrotic cells:tumor cells) at excision*
 
• PGA
 

Exploratory Objectives	Endpoints

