### 7.1.2. Treatment Termination

A summary of treatment termination will be provided for TL1 and TL2 using the safety population.

Descriptive statistics will be provided for the following parameters:

- Days to Necrosis where Days to Necrosis = Earliest Date of Necrosis of Lesion Specified – Treatment Start Date.
- Total Dose to Necrosis (mg) where Total Dose to Necrosis = Sum of all Actual Injection Doses (mg) including Treatment Start Date up to but not including Earliest Date of Necrosis of Lesion Specified.

Necrosed lesions are defined as treated lesions recorded in EDC as necrosed during scheduled and unscheduled Study Treatment Administration visits.

The number and percentage of subjects will be provided for the following parameters:

- Treatment Administered
- Treatment Not Applicable (TL2 only)
- Completed Treatment
- Lesion Not Necrosed
- Lesion Necrosed
- Treatment Discontinued
- Reason for Treatment Discontinuation (Adverse Event, Withdrawal of Consent, Lost to Follow-up, Death, Pregnancy, Subject Noncompliance, Sponsor Terminated Study, Investigator Decision, Other)

- Reason for Treatment Non-administration (Adverse Event, Withdrawal of Consent, Lost to Follow-up, Death, Pregnancy, Subject Noncompliance, Sponsor Terminated Study, Investigator Decision, Other) (TL2 only)

A separate listing will be provided for Treatment Termination using the Safety Population, and the listing will include TL1 Treated (Yes, No), Date of Last TL1 Treatment, Reason TL1 Treatment Not Done or Terminated (Adverse Event, Withdrawal of Consent, Lost to Follow-up, Death, Pregnancy, Subject Noncompliance, Completed Treatment, Sponsor Terminated Study, Investigator Decision, Other) with Specified Reason, TL2 Treated (Yes, No, Not Applicable), Date of Last TL2 Treatment, and Reason TL2 Treatment Not Done or Terminated (Adverse Event, Withdrawal of Consent, Lost to Follow-up, Death, Pregnancy, Subject Noncompliance, Completed Treatment, Sponsor Terminated Study, Investigator Decision, Other) with Specified Reason.

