### **8.4. Abscopal Effect Based on Non-treated Lesions at Excision**

An abscopal effect is a phenomenon whereby the treatment of target lesions leads to improvement in both treated and non-treated lesions.

A summary of (a) histologic clearance and (b) clinical clearance for non-treated lesions will be provided to investigate a possible abscopal effect using EOT data and the full analysis population.

The histologic clearance will follow Section 8.1 of this SAP except for using the histologic diagnosis of excised non-treated lesions (NTL1, NTL2, NTL3), and the clinical clearance will follow Section 8.2 of this SAP except for using the PGA of non-treated lesions (NTL1, NTL2, NTL3). The summary will be provided by clearance (Histologic, Clinical) within lesion (NTL1, NTL2, NTL3). The summary will also be run using the per-protocol population as outlined in Section 6 of this SAP.

A separate listing will be provided for the excision of all lesions as described in Section 8.1 of this SAP, and a separate listing will be provided for the PGA of all lesions as described in Section 8.2 of this SAP.

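### The TL2 tumour-volume summary in SAP 8.3, and its rerun in 8.7, does not require that TL2 was injected, so its mean and 95% CI can mix injected and uninjected tumours

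*SAP*

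**What the plan says.** **Tumour volume.** SAP 8.3 says that a summary of remaining volume, repeated for reduction in volume, "will be provided using descriptive statistics for excised lesions (TL1, TL2, NTL1, NTL2, NTL3) from the end-of-treatment (EOT) visit". The population is FA, with a per-protocol repeat, and the mean carries a 95% CI. SAP 8.7 reruns this summary after filling missing EOT values with the worst value reported, for any lesion that had a screening biopsy.

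**Clearance.** SAP 8.1, 8.2 and 8.6 cover TL1 and TL2 as well, but each limits itself to treated lesions. SAP 8.3 carries no such limit.

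**Abscopal effect.** The endpoint in SAP Section 2 for Part 2 is "clinical and histological clearance of nontreated lesions at excision if nontreated lesions exist". SAP 8.4 carries it out "using the histologic diagnosis of excised non-treated lesions (NTL1, NTL2, NTL3", the three nontarget labels, and handles clinical clearance in the same way.

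**Definitions.** The protocol glossary describes a nontreated lesion as "Target lesion that was not treated with VP-315" and, in a separate entry, a nontarget lesion as "BCC lesion to be observed for abscopal effect". Protocol 5.4 adds that "any eligible lesions that do not receive treatment (up to 3) will be tracked as nontarget lesions for abscopal effect".

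**Untreated TL2.** SAP 7.1.2 tabulates, for TL2 only, "Reason for Treatment Non-administration". Its listing separates a TL2 that was not treated from one to which treatment did not apply.

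**The concern.** A row labelled TL2 in an efficacy table will be read as the result in a second injected tumour. If some of those tumours never received drug, the row describes neither injected nor uninjected lesions. If uninjected lesions keep more viable tumour, the row understates the volume effect of injection and its interval is usually wider. Tumour volume is a secondary efficacy endpoint in Part 2, and results are shown by small cohort, where one lesion has weight. The same uninjected lesion also drops out of the abscopal summary, although two protocol passages point it there.

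**Working it through.** The documents give no count of uninjected TL2s and no expected volumes, so there is no plan figure to reproduce. The check has two parts.

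**1. Can an uninjected TL2 reach the TL2 row?**

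- *It can exist.* SAP 7.1.2 records it and lists reasons such as adverse event, withdrawal of consent and investigator decision.
- *One route is a reaction while TL1 is being treated.* Protocol 10.2 and SAP 5.9 end dosing after a DLT or TRAE SI. Protocol 7.3.1 and 7.3.2.2 have the medical monitor decide whether treatment continues after a TRAE SI. These passages conflict and must be reconciled, so how often this route applies is open. It was empty for DLTs in Part 1, where none occurred (Protocol 7.3.2.2).
- *Another route is a TL1 that is slow to necrose.* In Part 1 and Part 2 Cohorts 1 and 2, TL1 is treated first, within a two-week maximum. This covers 10 + 6 + 3 = 19 subjects by SAP 3.1, 3.3 and 3.4. It does not apply to Cohorts 4 and 5, where the start of TL2 does not depend on TL1 necrosis.
- *It is excised.* Protocol 8.3 requires excision of all target and nontarget lesions, also after early discontinuation of drug.
- *Its subject is in the FA population.* SAP 6 asks for a full dose in one treated lesion and one histologic clearance observation.

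Such a lesion therefore has an EOT volume in an FA subject and keeps the label TL2, so SAP 8.3 counts it in the TL2 row. If its EOT value is missing but it was biopsied at screening, SAP 8.7 gives it the worst-case volume in the same row.

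**2. How far does the row move?**

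Let *n* be the TL2 lesions in a row, *k* the uninjected ones, and *m1* and *m0* the mean remaining volume in injected and uninjected lesions.

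Pooled mean = [(n − k)·m1 + k·m0]/n, so shift = (k/n)·(m0 − m1).

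Assumed pairs (m1, m0) are (30, 70), (20, 80) and (15, 95), which give gaps of 40, 60 and 80 percentage points.

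| n | k | gap 40 | gap 60 | gap 80 |
|---|---|---|---|---|
| 3 | 1 | 13.3 | 20.0 | 26.7 |
| 6 | 1 | 6.7 | 10.0 | 13.3 |
| 10 | 1 | 4.0 | 6.0 | 8.0 |
| 10 | 2 | 8.0 | 12.0 | 16.0 |
| 15 | 1 | 2.7 | 4.0 | 5.3 |
| 15 | 3 | 8.0 | 12.0 | 16.0 |

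Each subject has at most one TL2, so *n* cannot exceed the group size: 3 in Cohort 2, 6 in Cohort 1, 10 in Part 1 and in each initial Cohort 4 and 5 group, and 26 and 27 in the expansions. Not every subject has a TL2, so actual *n* will often be smaller.

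For the interval, take n = 10, k = 2, means 20 and 80, and an assumed within-group SD of 25.

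- Expected pooled variance = 25² + [k(n − k)/n]·60²/(n − 1) = 625 + 1.6 × 3600/9 = 625 + 640 = 1265.
- Pooled half-width = t(0.975, 9)·√(1265/10) = 25.4, so the row reads 32.0 ± 25.4.
- For the 8 injected lesions alone, half-width = t(0.975, 7)·25/√8 = 20.9, so the row reads 20.0 ± 20.9.

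If reduction is taken as 100 minus remaining volume, it shifts by the same amount in the other direction.

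**The case against.** The strongest reply is that Protocol 5.4 already settles the matter: an eligible lesion that receives no treatment is followed as a nontarget lesion, so an uninjected TL2 belongs with the NTLs. That reading is possible, but the SAP has no rule that relabels the lesion, and 7.1.2 keeps it as TL2. Relabelling would not always fit either. A subject with two target and three nontarget lesions would have four untreated lesions for three NTL labels.

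Other replies stand in part.

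- The protocol's volume endpoint is not limited to treated lesions, so SAP 8.3 does not breach it. The defect is the mixing within one row.
- The analyses are descriptive, and a reader could find these lesions by matching the treatment-termination listing to the excision listing. The excision listing as specified does not show treated status, so this is work by hand and leaves the table unchanged.
- A reader might infer that every target-lesion efficacy summary ignores exposure. The wording of SAP 8.1, 8.2 and 8.6 does not support that.
- A reader might infer that SAP 8.4 is wrong to use NTL1 to NTL3. It is not. The glossary's nontarget entry, Protocol 8.2 and the Cohorts 1 and 2 endpoint in Protocol 3 all tie nontarget lesions to the abscopal effect. Taken alone, the glossary's nontreated entry would exclude every NTL, which cannot be intended. The gap is only the uninjected TL2.

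**Conclusion.** The point holds for the TL2 volume rows in SAP 8.3 and their rerun in 8.7, with a smaller gap in 8.4. As written, the plan lets injected and uninjected tumours share one mean and one 95% CI. The arithmetic shows the sensitivity, not the actual error: the number of uninjected TL2s, both means and the SD are assumed. The direction assumes that uninjected lesions keep more viable tumour. If no TL2 went uninjected, or the gap is small, little changes. The effect matters most in Part 1, Cohorts 1 and 2 and the initial groups of Cohorts 4 and 5.

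One might go further and say that the trial's treated and comparator lesion sets are both misassigned. The documents do not support that. They name no comparator and plan no treated-versus-untreated contrast, the NTLs are correctly placed, and TL1, the lesion every subject is to have, is not shown to be affected. Nor does every TRAE SI necessarily leave TL2 uninjected, given the conflicting passages on continuing treatment.

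**What to change.** In SAP 8.3 and 8.7, restrict the TL1 and TL2 volume rows to lesions that received VP-315, using the per-lesion injection data already in EDC (SAP 7.1.2 and 7.6). State that any VP-315 counts, in line with the glossary's treated-lesion entry, and that the full-dose condition remains a subject-level rule for FA membership. Show any uninjected TL2 in a separate row, labelled *TL2, not injected*, in 8.3 and beside NTL1 to NTL3 in 8.4. Apply the same split to values imputed under 8.7. Give the number of injected and uninjected TL2s per cohort. Sections 8.1, 8.2 and 8.6 need no change of substance.

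The cost is one derivation rule and one extra row, to be added before database lock as SAP 1 requires. The downside is slightly smaller TL2 denominators.
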